8. ADVERSE SAFETY EVENTS

Each eye treated must be examined for the presence or absence of adverse safety events at all visits, whether scheduled or not. The collection of safety events begins at the time the subject signs the informed consent form. Refer to Table 2 for instructions on events that require expedited reporting to the Sponsor.

For the purposes of this study, adverse safety events are defined broadly to include a range of events encompassing four hierarchical categories of risk, Adverse Events (AE), Unanticipated Adverse Device Effects (UADE), Complications/Potential Adverse Events, and Symptoms, each having an associated level of required CRF/IRB/Sponsor/FDA reporting (See Table 2 Table 2. Safety Event Reporting, "Safety Event Reporting").

The first category, AEs, represents the key safety events that are surveilled during the study (**Section 8.1**). The second category (**Section 8.2**), UADEs, represent rare unanticipated safety events directly attributable to the device.

	Symptoms	Complications/ Possible AEs	Adverse Events	UADEs	
Required Action			Record in AE CRF within 48 hours	Record in AE CRF and on UADE form within 48 hours	
	Recorded in Subject Questionnaires	Recorded in Postoperative CRFs	Investigator	Investigator reports to IRB within 10 working days or per IRB policy, whichever is shorter	
		Repo per II			Reports to IRB per IRB policy

Table 2. Safety Event Reporting

Tertiary safety events include anticipated Complications/Possible Adverse Events known to occur following laser refractive surgery (Section 8.4), and subjective Symptoms reported by subjects (Section 8.5).

A representative list of safety events that are associated with each risk category are summarized in Sections 8.1–8.5 below:

8.1 Adverse Events

An adverse event (AE) as defined in ISO standard 14155 is "any untoward medical occurrence, unintended disease or injury, or untoward clinical signs (including abnormal laboratory findings) in subjects, users, or other persons, whether or not related to the investigational medical device."

The following AEs are the key safety events surveilled during the study. Each occurrence of these AEs must be reported to the Sponsor by recording in the AE CRF within 48 hours, and in addition, must be reported to the IRB per IRB policy (See Table 2).

- Loss of > 2 lines (10 letters) BSCVA
- BSCVA worse than 20/40
- BSCVA worse than 20/25 if 20/20 or better preoperatively
- Haze \geq trace with loss of BSCVA > 2 lines (10 letters)
- Increased manifest refractive astigmatism > 2.0 D
- Corneal epithelial defect involving the keratectomy at one month or later
- Melting of the flap
- Miscreated flap (lost, incomplete, too thin)
- Diffuse lamellar keratitis (Grade 3 or above) ⁴²
- Corneal infiltrate or ulcer
- Any persistent corneal epithelial defect at one month or later
- Epithelium in the interface with loss of 2 lines (10 letters) or more best spectacle corrected visual acuity (BSCVA)
- Intraocular Pressure (IOP) with increase of >10 mmHg above baseline on two consecutive examinations or an IOP greater than 30 mmHg on two consecutive examinations
- Haze beyond 6 months with loss of 2 lines or greater (≥ 10 letters ETDRS) of BSCVA
- Decrease in BSCVA of greater than or equal to 2 lines (≥ 10 letters ETDRS) not due to irregular astigmatism as shown by rigid contact lens refraction at 3 months or later
- Retinal detachment
- Corneal Edema at 1 month or later
- Retinal vascular accidents
- Any other vision-threatening event
- Ocular penetration

8.2 Unanticipated Adverse Device Effects (UADE)

UADEs are considered to be rare, unanticipated events and have a serious effect on health or safety or represent any life-threatening problem or death caused by the device, if the event has not previously been identified in the investigational plan or in Section 8.1 or Section 8.4. Each occurrence of an UADE must be recorded in both the AE & UADE CRFs within 48 hours of occurrence. Investigators have 10 working days to report the occurrence of a UADE to the Sponsor (via UADE CRF), and thereafter the Sponsor has 10 working days to report the UADE to the FDA, the IRB and all study Investigators. (see Table 2Table 2. Safety Event Reporting, "Safety Event Reporting") as described in 21 CFR 812.150(b)(1). UADEs may include, but are not limited to, the following events:

- Device related death
- Enucleation of treated eye
- Corneal transplant of treated eye

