3.3 Risk/Benefit Analysis of LASIK

The risks of performing LASIK on sighted eyes include improper correction, decrease in BSCVA, glare, halo, foreign body sensations, corneal scarring, corneal ulceration or perforation, intraocular infection, corneal decompensation, persistent corneal edema, hyphema, hypopyon, endophthalmitis, microbial keratitis,³² cataract, epithelium in the interface, lost / misplaced / misaligned flap, dry eye, or melting of the flap.

Steps taken to mitigate the risks associated with this protocol include

- enlisting only Investigators with prior training and experience in corneal refractive surgery, including experience with: (a) the use of femtosecond laser "flap makers" and (b) laser-assisted in situ keratomileusis (LASIK) ensuring that Investigators review and understand this investigational protocol; and
- monitoring the study for adherence to the protocol and verifying all incidences of adverse effects are reported. During the period when study procedures and/or study sites are interrupted by the COVID-19 pandemic (see Section 7.4.1.1), monitoring may occur remotely.

The principle benefit of an aspheric LASIK procedure is the potential freedom from or reduced dependence on spectacles (glasses) and/or contact lenses for the correction of refractive error. LASIK may be safer than contact lens wear in the long term.²³ Additional potential benefits include rapid visual recovery and stabilization of refraction, and reduced risk of iatrogenic corneal stromal irregularity due to scanning of small overlapping beam.

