6.5.8.3 Adverse Events and Unanticipated Adverse Device Effects

An AE is defined as any untoward medical occurrence, unintended disease or injury, or untoward clinical signs (including abnormal laboratory finds) in subjects, users, or other persons, whether or not related to the investigational medical device.

The following AEs are the key safety events surveilled during the study in order to assess conformity to the target values of "Incidence of Adverse Events".

- Loss of > 2 lines (10 letters) BSCVA
- BSCVA worse than 20/40
- BSCVA worse than 20/25 if 20/20 or better preoperatively
- Haze \geq trace with loss of BSCVA > 2 lines (10 letters)
- Increased manifest refractive astigmatism > 2.0 D
- Corneal epithelial defect involving the keratectomy at one month or later
- Melting of the flap
- Miscreated flap (lost, incomplete, too thin)
- Diffuse lamellar keratitis (Grade 3 or above)
- Corneal infiltrate or ulcer

- Any persistent corneal epithelial defect at one month or later
- Epithelium in the interface with loss of 2 lines (10 letters) or more BSCVA
- IOP with increase of > 10 mmHg above baseline on two consecutive examinations or an IOP greater than 30 mmHg on two consecutive examinations
- Haze beyond 6 months with loss of 2 lines or greater (≥ 10 letters ETDRS) of BSCVA
- Decrease in BSCVA of greater than or equal to 2 lines (≥ 10 letters ETDRS) not due to irregular astigmatism as shown by rigid contact lens refraction at 3 months or later
- Retinal detachment
- Corneal edema at 1 month or later
- Retinal vascular accidents
- Ocular penetration
- Other ocular event

All UADEs are considered to be rare, unanticipated events and have a serious effect on health or safety or represent any life-threatening problem or death caused by the device, if the event has not previously been identified in the investigational plan. A UADE may include, but is not limited to, the following events:

- Device-related death
- Enucleation of treated eye
- Corneal transplant of treated eye

A summary (counts and percentages) of AEs/UADEs will be presented by incidence of AEs for operative visit, each postoperative study visit, and overall (a Total column) using all treated eyes. At a study visit subjects' eyes will be counted only once if they experience multiple AEs/UADEs of the same type and similarly will be counted only once in Total column if they have AEs/UADEs of the same type at multiple study visits.

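### The UADE exclusion in Protocol 8.2 conflicts with the open vision-threatening line in 8.1, and the SAP replaces that line without declaring it

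*Protocol*

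**What the plan says.** Protocol 8.2 defines a UADE as a rare, unanticipated event, caused by the device, that is serious, life-threatening or fatal. It adds a condition: the event qualifies "if the event has not previously been identified in the investigational plan or in Section 8.1 or Section 8.4". It then gives three examples, introduced by "UADEs may include, but are not limited to, the following events":

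- "Device related death"
- "Enucleation of treated eye"
- "Corneal transplant of treated eye"

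Protocol 8.1 lists the key adverse events. Most lines are specific, but one is open: "Any other vision-threatening event".

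SAP 6.5.8.3 reproduces the key AE list for tabulation. The open vision-threatening line is not in it, and the list ends instead with "Other ocular event". The SAP's UADE definition carries the same exclusion but refers only to the investigational plan. The effect is the same, because Sections 8.1 and 8.4 are part of that plan. SAP 6.6, which records departures from the protocol, does not mention the altered AE line.

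**The concern.** A definition that turns on whether an event has already been identified needs a closed list to test against. An open category in that list blurs the test, because anything that threatens vision can be said to be identified already, however unforeseen it was. Vision-threatening device effects are a main class of events that UADE reporting exists to catch in a refractive laser study.

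The practical stake is classification at the site. Two investigators with the same event could file it differently and each point to the text. The choice decides whether the UADE form is completed and whether the Sponsor's timed notice to FDA, the IRB and all Investigators is triggered. The study is open label and single arm, runs at up to 12 sites and has no data monitoring committee (SAP 6.5.7.3). That notice is the only timed message to all Investigators set out in Section 8.

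The SAP raises a separate, smaller question: whether the final AE table would show unlisted vision-threatening events as such.

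**Working it through.** No arithmetic underlies the point beyond simple counts. The check sets the texts side by side.

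**1. Apply 8.2's condition to 8.2's own examples.**

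| Example in 8.2 | Vision-threatening, so within the open line in 8.1? | UADE on the literal test? | Offered by 8.2 as a possible UADE? |
|---|---|---|---|
| Death related to the device | No | Yes | Yes |
| Enucleation | Yes | No | Yes |
| Corneal transplant | Yes | No | Yes |

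The literal test contradicts the section in two of three examples. Device-related death, and non-ocular life-threatening effects generally, are untouched, because the open line covers vision only.

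**2. Compare the reporting routes** (Protocol 8.1, 8.2 and what can be read of Table 2).

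| Step | Filed as AE only | Filed as UADE |
|---|---|---|
| Site record | AE CRF within 48 hours | AE and UADE CRFs within 48 hours |
| Investigator to Sponsor | Through that AE CRF entry | Through the UADE CRF, within 10 working days |
| Investigator to IRB | Per IRB policy | 10 working days or IRB policy, whichever is shorter |
| Sponsor onward | None stated in 8.1 | FDA, IRB and all Investigators within 10 further working days |

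The 48-hour step is common to both routes. Three things depend on classification: the UADE form, the fixed IRB limit and the Sponsor's onward report. As a UADE, the event has a stated outer limit of 10 + 10 = 20 working days to reach FDA and all Investigators. As an AE, 8.1 states none.

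**3. Compare the two AE lists.** Protocol 8.1 has 20 lines and SAP 6.5.8.3 has 20 lines. Nineteen correspond. The remaining one is the open vision-threatening line in the protocol and "Other ocular event" in the SAP.

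**4. Look for the change in SAP 6.6.** That section records items as small as renaming UDVA to UCDVA, and several safety changes (Schirmer's test, IOP, contrast sensitivity). The AE-list substitution is not among them.

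**5. Ask what the SAP still shows.** SAP 6.5.8.2 tabulates by eCRF category and gives MedDRA-coded terms in the listings. SAP 6.5.8.3 lists every AE and UADE by subject and adds one count, with an exact 95% CI, of eyes with a serious device-related AE. An unlisted vision-threatening event would therefore be traceable in the listing. It would enter the aggregate count if serious and device-related, but that count does not isolate vision-threatening events.

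**The case against.** The strongest reply is that 8.2 answers itself. It names enucleation and corneal transplant as UADEs in an open list, so its authors evidently did not mean the catch-all to pre-empt UADE status, and Section 8 calls the lists representative. Strict literalism would also exclude all three examples merely because 8.2, part of the plan, names them. This stands as evidence of intent, so a reader should not infer that every unlisted vision-threatening event is removed from UADE status. It does not supply a rule for an event that is neither named in 8.2 nor foreseen, and there the two sections still point in opposite directions.

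A reader might also infer that such events lose expedited reporting altogether. They do not: the 48-hour Sponsor report and the IRB report remain. The medical monitor reviews safety signals across sites (10.1), and adverse trends may go to the IRB and FDA (10.4). Neither of these is a timed, event-level notice.

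It is tempting to cite the risks in Protocol 3.3, such as "intraocular infection, corneal decompensation, persistent corneal edema, hyphema, hypopyon, endophthalmitis", as UADEs lost through the catch-all. They are named in the plan, so they count as identified with or without it. It is likewise tempting to require that identification mean identification at the expected severity and frequency. The documents state no expected AE rates against which such a test could be run.

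On the SAP, the objection is that only tabulation is affected and that the complications list in 6.5.8.4 has its own residual row for other events. It is therefore not shown that grave and minor unlisted events would share one row. That stands. The missing row and the missing declaration remain.

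**Conclusion.** The point holds as an internal contradiction in a safety-reporting rule, together with an undeclared change to the SAP's AE list. Two of 8.2's three examples conflict with its own condition. Three reporting elements depend on how a site resolves the conflict, and one of 20 key AE lines differs between protocol and SAP without explanation. No primary endpoint, hypothesis test or sample size is affected. Few events are likely, though the documents give no rate. The change is worth making because each such event matters and the correction is small.

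The conclusion rests on three assumptions:

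- Enucleation and corneal transplant count as vision-threatening.
- The reporting steps in Table 2 are as they can be read. The table is damaged in the available text, so its full AE column cannot be checked.
- The table rows follow the SAP's list. SAP 6.5.8.2 says they follow eCRF categories, and the eCRF is not available. If it has a vision-threatening category, the tabulation point reduces to an inconsistency between documents.

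**What to change.** - **Protocol 8.2:** add a sentence stating that an event covered by Section 8.1 only through the line "Any other vision-threatening event" does not count as previously identified. This reconciles 8.1 with 8.2 and with its examples. The SAP's UADE definition should carry the same clarification or refer to 8.2.
- **SAP 6.5.8.3:** restore the vision-threatening line as its own row, separate from "Other ocular event". At minimum, declare and explain the replacement in SAP 6.6.

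The cost is one sentence, one table row and, if the eCRF lacks it, one category. A few more events may go through UADE review. No analysis of effectiveness changes.

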8.3 Reporting Device Deficiencies

A device deficiency is defined as an inadequacy of a medical device with respect to its identity, quality, durability, reliability, safety or performance. Device deficiencies include malfunctions, use errors, and inadequate labeling.

Investigators must evaluate, record, and report via applicable forms any complaints/deficiencies or malfunctions experienced with Test Device during this trial to the Sponsor or its representative promptly. The Sponsor shall review all device deficiency reports and, upon the Sponsor's request, Investigators must supply any additional information related to the safety reporting of a particular event.

The contact for reporting device deficiencies is:

8.4 Complications / Possible Adverse Events

Complications / possible adverse events are known to potentially occur in association with laser refractive surgery and include the safety events listed below. Each occurrence of these safety events will be recorded in the postoperative CRFs only and will not be reported to the Sponsor or the IRB (See Table 2, "Safety Event Reporting"):

- Allergic conjunctivitis
- Blepharitis
- Conjunctivitis
- Corneal abrasion
- Corneal edema between 1 week to less than 1 month after procedure
- Corneal flap lifting between 1 day to 1-month post-surgery for wrinkled flap
- Corneal haze

- Corneal scar
- Debris in the interface
- Diffuse lamellar keratitis (grade 2 or less) ⁴²
- Double/ghost images in operative eye
- Dry eye
- Enhancement not done due to flap fibrosis
- Epithelium at the flap edge
- Epithelium in the interface
- Flap is not of the size and shape as initially intended or resultant flap is misaligned
- Foreign body sensation at 1 month or later
- Iritis
- Loose epithelium
- Meibomian gland dysfunction
- Mucus under edge of flap
- Pain at 1 month or later
- Peripheral corneal epithelial defect at one (1) month or later
- Possible allergic reaction to plugs or eye drops
- Postoperative flap complications
- Punctal plug inserted
- Punctal plug replaced
- Rough epithelium
- Superficial punctuate keratopathy (SPK)
- Steroid induced IOP increase
- Subconjunctival hemorrhage
- Transient light-sensitivity syndrome (TLSS)
- Trace microstriae
- Trace corneal haze
- Vitreous floaters

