7.1.2.4 Immediately Post-Surgery

The treated eyes are managed with medications (e.g., topical antibiotics, analgesic and anti-inflammatory drops, and any other medicines prescribed at the physician's discretion),

bandage contact lens, and/or punctal plugs as per the treating physician's usual regimen. The subject is instructed to return in 24 hours to begin post-operative evaluations.

7.1.3 Post-operative Visits – Days 1 to Month 9

Subjects will be followed for six (6) post-operative visits. Recording of ocular medications used for subject eyes enrolled and any AEs or complications/possible AEs in the subject source document and appropriate eCRF must be continued throughout the course of the study. Each eye that is enrolled is examined independently.

The following measures are to be included at the follow-up in-clinic examinations for all treated eyes of participating subjects. If a subject cannot receive timely safety assessments due to the COVID-19 pandemic, protocol deviations will occur and the processes described in **Section 7.1.3.5** and **Section 7.4.1.2** are to be followed until such time as the subject can be seen at an in-clinic visit and planned examinations can occur within the appropriate visit windows (see **Appendix A**):

7.1.3.1 Day 1 Post-operative – Visit 3

- AE and complication/possible AE recording, all treated eyes
- Any change in Concomitant Medications
- UCNVA and UDVA, photopic conditions
- Slit lamp examination

7.1.3.2 Week 1 Post-operative (all enrolled eyes) – Visit 4

- AE and complication/possible AE recording, all treated eyes
- Any change in Concomitant Medications
- Manifest refraction (sphere/cylinder/axis)
- UCNVA, UDVA and BSCVA, photopic conditions
- Slit lamp examination

7.1.3.3 Month 1 Post-operative (all enrolled eyes) – Visit 5

- AE and complication/possible AE recording, all treated eyes
- Any change in Concomitant Medications
- Corneal topography
- Manifest refraction (sphere/cylinder/axis)
- UCNVA, UDVA and BSCVA, photopic conditions
- Slit lamp examination
- Tonometry

7.1.3.4 Months 3, 6, 9 Post-operative (all enrolled eyes) – Visits 6, 7, and 8²

- Post-operative PROWL questionnaire ³⁵
- AE and complication/possible AE recording, all treated eyes

² Further details for the study visits and procedures can be found in **Appendix A** and **Appendix B**.
- Any change in Concomitant Medications
- Manifest refraction (sphere/cylinder/axis)
- Specular microscopy sub-study (only at Month 6)³

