7.3 Concomitant Medications/Therapy

The Investigator may use any medications or treatment that is judged necessary, appropriate, and beneficial to the subject.

Documentation of all medications used by the subject during this study for the treatment of operative eyes (with the exception of the surgeon's standard regimen for pre-, intra- and post-operative medications) will be made on the appropriate sections of the eCRFs.

7.4 **Protocol Deviations**

As required under §21 CFR 56.108(a)(3)&(4), an Investigator should notify the Sponsor and reviewing IRB of any deviation from the investigational plan intended to protect the life or physical well-being of a subject in an emergency. The date of and reason for protocol deviations will be documented in all cases. Significant or major protocol deviations affecting the safety, rights, and welfare of the subject or the integrity of the study must be reported by the Investigator to the IRB immediately. Reporting of all other protocol deviations must adhere to the requirements of the governing IRB.

Protocol assessments will continue until the end of the study, unless the protocol deviations put the subject at risk or the subject's condition requires that he/she should be discontinued from the study.

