6.5.5 Concomitant Medications

Concomitant medications are medications listed for a subject as having been taken (1) prior to LASIK surgery and continuing for any time following the surgery or (2) at any time following LASIK surgery. Concomitant medications will be coded using World Health Organization Drug Dictionary (WHODrug) terminology, Version B3 Global March 2019. However, medications will not be summarized in tables.

In addition, the Investigator may use any medication that is judged necessary, appropriate, and beneficial to the subject. Documentation of all such medications used by the subject during this study for the treatment of operative eyes (with the exception of the surgeon's standard regimen for pre-, intra-, and post-operative medications) will be made on the appropriate sections of the electronic case report forms (eCRFs).

A data listing by subject that includes all concomitant medications will be provided. The concomitant medication listing will not contain information on non-drug therapies.

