6.5.8.4 Complications/Potential Adverse Events

Complications/Possible AEs are known to potentially occur in association with laser refractive surgery and include the safety events listed below:

- Allergic conjunctivitis
- Blepharitis
- Conjunctivitis
- Corneal abrasion
- Corneal edema between 1 week to less than 1 month after procedure
- Corneal flap lifting between 1 day to 1 month post-surgery for wrinkled flap
- Corneal haze
- Corneal scar
- Debris in the interface
- Diffuse lamellar keratitis (grade 2 or less)
- Double/ghost images in operative eye
- Dry eye
- Enhancement not done due to flap fibrosis
- Epithelium at the flap edge
- Epithelium in the interface
- Flap is not of the size and shape as initially intended or resultant flap is misaligned
- Foreign body sensation at 1 month or later
- Iritis
- Loose epithelium
- Meibomian gland dysfunction

- Mucus under edge of flap
- Pain at 1 month or later
- Peripheral corneal epithelial defect at 1 month or later
- Possible allergic reaction to plugs or eye drops
- Postoperative flap complications
- Punctal plug inserted
- Punctal plug replaced
- Rough epithelium
- Superficial punctate keratopathy (SPK)
- Steroid induced IOP increase
- Subconjunctival hemorrhage
- Transient light-sensitivity syndrome (TLSS)
- Trace microstriae
- Trace corneal haze
- Vitreous floaters
- Other

Complications/potential AEs will be summarized in a similar manner as AEs/UADEs for operative visit, each postoperative visit, and overall (a Total column) using all treated eyes.

All complications/potential AEs also will be presented in a data listing by subject. The complications/potential AEs leading to study discontinuation will be listed separately.

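### Punctal plugs are permitted as part of usual postoperative care, yet every plug counts as a complication, so the plug rows partly reflect surgeon habit

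*Protocol*

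**What the plan says.** Protocol 7.1.2.4 describes care immediately after surgery. Besides medications, it allows "bandage contact lens, and/or punctal plugs as per the treating physician's usual regimen". No indication is attached.

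Protocol 8.4 lists complications and possible adverse events. Two of the items are "Punctal plug inserted" and its counterpart for replacement. The recording rule is "Each occurrence of these safety events will be recorded in the postoperative CRFs only". Dry eye is a separate item in the same list.

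SAP 6.5.8.4 repeats both plug items unchanged and adds: "Complications/potential AEs will be summarized in a similar manner as AEs/UADEs for operative visit, each postoperative visit, and overall". The overall figure is a Total column, and the base is all treated eyes. A by-subject listing of all complications is also planned. SAP 6.5.8.3, whose method this follows, counts an eye once per event type at a visit and once per type in the Total column.

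Two passages deal with background treatment. Protocol 7.3 requires documentation of medications for operative eyes, "with the exception of the surgeon's standard regimen for pre-, intra- and post-operative medications". SAP 6.5.5 states: "The concomitant medication listing will not contain information on non-drug therapies".

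**The concern.** The same act is permitted background care in one section and a complication in another, and nothing says which applies when a plug is placed by routine. A surgeon who plugs every eye would report a complication in every eye. A surgeon who plugs only in response to a finding would report only those eyes.

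The study has one arm, so no control rate exists against which routine use would cancel. A reader of the safety table in the PMA supplement would see a plug rate under complications and could not tell how much of it followed a postoperative problem. At stake is the meaning of two descriptive safety rows.

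**Working it through.** There is no planned figure to reproduce, because the documents state no expected plug rate. The check is a comparison of text, followed by an illustration of size.

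**Text comparison**

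1. *Does 7.1.2.4 require a reason for a plug?* No. It defers to the surgeon's usual practice.
2. *Do 8.4 or SAP 6.5.8.4 restrict the plug items?* No. Other items in the same list are restricted. Pain and foreign-body sensation count only from one month. Corneal edema counts from one week to under one month. Flap lifting has both a time window and a stated reason. The plug items have neither.
3. *Does any other section exempt routine plugs?* No. The standard-regimen exception in Protocol 7.3, repeated in SAP 6.5.5, concerns documentation of medications, not recording of complications.
4. *Do the documents describe data that would separate the two uses?* Only in part. The operative report in Protocol 7.1.2.3 has no plug item, and the medication listing leaves out non-drug therapies. The complication data would show that a plug was placed and at which visit, but no section asks why.
5. *Which outputs are affected?* The plug-inserted and plug-replaced rows. The visit columns give some separation, since plugs placed at surgery would fall in the operative-visit column. The Total column combines all visits and gives none.

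**Illustration of size**

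Inputs:
- Treated eyes: 334 (Protocol 9.3.5).
- Eyes per site: at least 20, and at most 15% of total enrollment (Protocol 5.4).
- Sites: up to 12 (Protocol 5.4).
- Assumptions, not in the documents: a routine-plug site plugs every eye, and total enrollment is taken as 334.

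Share added to the Total column of the plug-inserted row = (number of such sites × eyes per site) / 334.

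| One site of this kind | Eyes | Share of 334 |
|---|---|---|
| Minimum size | 20 | 20/334 = 6.0% |
| Average of 12 sites | 334/12 = 27.8 | 27.8/334 = 8.3% |
| At the cap | 0.15 × 334 = 50.1, about 50 | 50/334 = 15.0% |

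With no such site, the addition is 0%.

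**The case against.** The strongest reply is that the plug row is labelled as a procedure and counts exactly what it says. Postoperative dry eye has its own row, as do superficial punctate keratopathy, meibomian gland dysfunction and late foreign-body sensation. Section 7.1.2.4 concerns the period immediately after surgery, and the SAP shows the operative visit in its own column, so much of the separation may already exist. A planned plug on Day 0 is arguably not a safety event at all, given that 8.4 refers to the postoperative forms only. Finally, no passage says that any site uses plugs routinely.

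Much of this stands. A reader might infer that the dry-eye rate is inflated; it is not, because dry eye is tabulated separately. A reader might also infer from the medication exemptions that plug use is invisible. The documents do not support that either: plugs have their own route through 8.4 and are listed by subject, and only the reason is missing. Nor do the documents show distorted dryness results. Under SAP 6.5.8.7, Schirmer's results are listed and not summarized. Comparing PROWL dryness scores by plug status would be confounded by indication and would set per-subject scores against per-eye treatment.

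The reply does not remove the conflict. The Day 0 reading is uncertain, because Protocol Appendix A marks complications for collection at Visit 2 and SAP 6.5.8.4 tabulates the operative visit. Plugs placed early after surgery remain ambiguous, and so does the whole Total column.

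**Conclusion.** The point holds as a defect in recording and reporting. Protocol 7.1.2.4, Protocol 8.4 and SAP 6.5.8.4 cannot all be followed without counting permitted routine care as a complication. The plug rows, and the Total column above all, therefore partly reflect surgeon habit. It would go too far to say that they reflect only habit, since plugs placed for a postoperative finding are in the same rows.

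The 6.0% to 15.0% for one site rests on the assumption that the site plugs every eye. It is an illustration, not an estimate, and the floor is 0%. No primary endpoint, hypothesis test or sample size is affected. SAP 6.5.8.3 ties its target values to adverse events, not to complications. The change is worth making because it is cheap and makes a reported safety rate interpretable, not because the study's conclusions depend on it.

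**What to change.** Reconcile Protocol 7.1.2.4, Protocol 8.4 and SAP 6.5.8.4. Record the reason for each plug insertion or replacement, and split the plug reporting in SAP 6.5.8.4 into two rows:

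- (a) plugs placed as the surgeon's planned regimen, reported as background treatment;
- (b) plugs inserted or replaced for a postoperative sign or symptom, kept as complications.

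Report both rows so that no event is lost. For eyes already treated, obtain the reason from source documents by query. Where the source does not give it, report the plug under (b), marked as reason unknown.

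The cost is one extra eCRF field, the queries, and reliance on the investigator's attribution. The eCRF is not among the documents; if it already captures the reason, only the protocol and SAP wording needs to change. The fix affects recording and reporting only and takes no position on whether plugs should be used. No change to the PROWL analysis or the Schirmer's listing is needed.
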